## 4 REGISTRATION PROCEDURES

## 4.1 Investigator and Research Associate Registration with CTEP

Food and Drug Administration (FDA) regulations require sponsors to select qualified investigators. National Cancer Institute (NCI) policy requires all individuals contributing to NCI-sponsored trials to register with their qualifications and credentials and to renew their registration annually. To register, all individuals must obtain a Cancer Therapy Evaluation Program (CTEP) Identity and Access Management (IAM) account at https://ctepcore.nci.nih.gov/iam. Investigators and clinical site staff who are significant contributors to research must register in the Registration and Credential Repository (RCR). The RCR is a self service online person registration application with electronic signature and document submission capability.

RCR utilizes five person registration types.

- Investigator (IVR): MD, DO, or international equivalent,
- Non Physician Investigator (NPIVR): advanced practice providers (e.g., NP or PA) or graduate level researchers (e.g., PhD),
- Associate Plus (AP): clinical site staff (e.g., RN or CRA) with data entry access to CTSU applications such as the Roster Update Management System [RUMS], OPEN, Rave, acting as a primary site contact, or with consenting privileges;
- Associate (A): other clinical site staff involved in the conduct of NCI-sponsored trials,

• Associate Basic (AB): individuals (*e.g.*, pharmaceutical company employees) with limited access to NCI-supported systems.

RCR requires the following documents outlined in Table 1:

**Table 1: RCR Required Documentation** 

Documentation Required	IVR	NPIVR	AP	A	AB
Form FDA 1572	•	•			
Financial Disclosure Form	~	✓	~		
NCI Biosketch (education, training, employment, license, and certification)	•	•	•		
Good Clinical Practice (GCP) Training	>	•	>		
Agent Shipment Form (if applicable)	~				
CV (optional)	~	~	~		

An active CTEP-IAM user account with a linked ID.me account (the latter required immediately for new CTEP-IAM accounts, and by July 1, 2023 for all users) is required to participate in the NCI clinical trials supported by the Cancer Trials Support Unit (CTSU) and to access all CTEP and CTSU websites and applications. In addition, IVRs and NPIVRs must list all clinical practice sites and Institutional Review Boards (IRBs) covering their practice sites on the FDA Form 1572 in RCR to allow the following:

- Addition to a site roster;
- Selection as the treating, consenting, treating, credit, or drug shipment investigator or consenting person in OPEN;
- Ability to be named as the Site-Protocol Principal Investigator (PI) on the IRB approval; and
- Assignment of the Clinical Investigator (CI) task on the Delegation of Tasks Log (DTL).

In addition, all investigators acting as the Site-Protocol PI (investigator listed on the IRB approval), consenting/treating/drug shipment investigator in OPEN, or as the CI on the DTL must be rostered at the enrolling site with a participating organization.

Additional information is located on the CTEP website at https://ctep.cancer.gov/investigatorResources/default.htm. For questions, please contact the RCR Help Desk by email at RCR Help Desk by email at <a href="htt

#### 4.2 CTSU Registration Procedures

Permission to view and download this protocol and its supporting documents is restricted and is based on person and site roster assignment housed in the CTSU Regulatory Support System (RSS).

This study is supported by the NCI Cancer Trials Support Unit (CTSU).

## 4.2.1 IRB Approval

U.S. sites participating in the PEP-CTN network are required to use the NCI CIRB as of March 1, 2019. Local IRB review Version Date: 02/02/2024 Page 24

will continue to be accepted for studies that are not reviewed by the CIRB, or if the study was previously open at the site under the local IRB. International sites should continue to submit Research Ethics Board (REB) approval to the CTSU Regulatory Office following country-specific regulations.

Questions about establishing site preferences can be addressed to the CTSU Regulatory Office by emailing the email address above or calling [name].

Sites using their local IRB or REB must submit their approval to the CTSU Regulatory Office using the Regulatory Submission Portal located in the Regulatory section of the CTSU website. Acceptable documentation of local IRB/REB approval includes:

- Local IRB documentation,
- IRB-signed CTSU IRB Certification Form, and/or
- Protocol of Human Subjects Assurance Identification/IRB Certification/Declaration of Exemption Form.

In addition, the Site Principal Investigator (Site PI) (*i.e.*, the investigator on the IRB/REB approval) must meet the following criteria for the site to be able to have an Approved status following to complete processing of the IRB/REB approval record:

- Have an Active CTEP status;
- Have an Active status at the site(s) on the IRB/REB approval (applies to US and Canadian sites only) and on at least one participating organization's roster;
- If using NCI CIRB, be active on the NCI CIRB roster under the applicable CIRB Signatory Institution(s) record;
- Include the IRB number of the IRB providing approval in the Form FDA 1572 in RCR profiles;
- Lists all sites on the IRB/REB approval as Practice Sites in Form FDA 1572 in the RCR profile; and
- Have the appropriate CTEP registration type for the protocol.

#### 4.2.2 Additional Requirements

Additional site requirements to obtain an approved site registration status include:

- An active Federal Wide Assurance (FWA) number;
- An active roster affiliation with the Lead Protocol Organization (LPO) or a Participating Organization;
- An active roster affiliation with the NCI CIRB roster under at least one CIRB Signatory Institution (US sites only);
   and
- Compliance with all applicable protocol-specific requirements (PSRs).

Note: Sites participating on the NCI CIRB initiative and accepting CIRB approval for the study are not required to submit separate IRB approval documentation to the CTSU Regulatory Office for initial, continuing or amendment review.

## 4.2.3 Submitting Regulatory Documents

Submit required forms and documents to the CTSU Regulatory Office using the Regulatory Submission Portal on the CTSU member's website.

To access the Regulatory Submission Portal, log in to the CTSU members' website, go to the Regulatory section and select Regulatory Submission.

Institutions with patients waiting that are unable to use the Regulatory Submission Portal should alert the CTSU Regulatory Office immediately by phone or email: [name], or <a href="https://creativecolorgraphics.org/regulatory-colorg

## 4.2.4 Delegation of Tasks Log (DTL)

Each site must complete a protocol-specific Delegation of Tasks Log (DTL) using the DTL application in the *Delegation Log* section on the CTSU members' website. The Clinical Investigator (CI) is required to review and electronically sign the DTL prior to the site receiving an approved site registration status and enrolling patients to the study. To maintain an approved site registration status the CI must re-sign the DTL at least annually and when a new version of the DTL is released; and to activate new task assignments requiring CI sign-off. Any individual at the enrolling site on a participating roster may initiate the site DTL. Once the DTL is submitted for CI approval, only the designated DTL Administrators or the CI may update the DTL. Instructions on completing the DTL are available in the Help Topics button in the DTL application and describe DTL task assignments, CI signature, and CTEP registration requirements, as well as include a Master Task List..

## 4.2.5 Checking Your Site's Registration Status

Site registration status may be verified on the CTSU members' website.

- Click on *Regulatory* at the top of the screen;
- Click on Site Registration; and
- Enter the sites 5-character CTEP Institution Code and click on Go:
  - o Additional filters are available to sort by Protocol, Registration Status, Protocol Status, and/or IRB Type.

Note: The status shown only reflects institutional compliance with site registration requirements as outlined within the protocol. It does not reflect compliance with protocol requirements for individuals participating on the protocol or the enrolling investigator's status with NCI or their affiliated networks.

#### **Requirements For PEP-CTN Site Registration**

IRB approval (For sites not participating via the NCI CIRB; local IRB documentation, an IRB signed CTSU IRB Certification Form, Protocol of Human Subjects Assurance Identification/IRB Certification/IRB Certification/Declaration of Exemption Form

## 4.3 Patient Enrollment

Investigators should refer to the COG website to determine if the study is currently open for accrual.

## **4.3.1** OPEN

Patient enrollment for this study will be facilitated using the Slot Reservation System in conjunction with the registration system in Oncology Patient Enrollment Network (OPEN).

Requirements for OPEN access:

• A valid CTEP-IAM account and linked ID.me account (ID.me accounts are required for all newly created

CTEP-IAM accounts and by July 1, 2023 for all users);

- To perform enrollments or request slot reservations: Must be on an LPO roster, ETCTN corresponding roster, or participating organization roster with the role of Registrar. Registrars must hold a minimum of an Associate Plus (AP) registration type;
- If a Delegation of Tasks Log (DTL) is required for the study, the registrar) must hold the 'OPEN Registrar' task on the DTL for the site; and
- Have an approved site registration for the protocol prior to patient enrollment.

Access OPEN at https://open.ctsu.org or from the OPEN link on the CTSU members' website. Further instructional information is in the OPEN section of the CTSU website at https://open.ctsu.org. For any additional questions, contact the CTSU Help Desk at [name] or ctsu.org. For any additional questions, contact the CTSU Help Desk at [name] or ctsu.org. For any additional questions, contact the CTSU Help Desk at [name] or ctsu.org. For any additional questions, contact the CTSU Help Desk at [name] or ctsu.org. For any additional questions, contact the CTSU Help Desk at [name] or ctsu.org.

Prior to accessing OPEN, site staff should verify the following:

- Patient has met all eligibility criteria within the protocol stated timeframes; and
- All patients have signed an appropriate consent form and Health Insurance Portability and Accountability Act (HIPAA) authorization form (if applicable).

*Note*: The OPEN system will provide the site with a printable confirmation of registration and treatment information. Please print this confirmation for your records.

Access OPEN at https://open.ctsu.org or from the OPEN link on the CTSU members' website. Further instructional information is in the OPEN section of the CTSU website at https://open.ctsu.org. For any additional questions, contact the CTSU Help Desk at [name] or ctsu.org or https://open.ctsu.org. For any additional questions, contact the CTSU Help Desk at [name] or ctsu.org or testcoordinates or <a href="testc

#### 4.3.2 Patient Registration

Prior to enrollment on study, patients must be assigned a COG patient ID number. This number is obtained via the COG Registry in the OPEN system once authorization for the release of protected health information (PHI) has been obtained.

If you have problems with the registration, please refer to the online help. For additional help or information, please contact the CTSU Help Desk at [name] or [contact].

## 4.3.3 Reservation and Contact Requirements

Prior to enrolling a patient, a reservation must be made following the steps below and the Study Chair or Vice Chair notified. (The patient will need a COG patient ID number in order to obtain a reservation). Reservations may be obtained 24 hours a day through the Oncology Patient Enrollment Network (OPEN) system. Patients must be enrolled within 7 calendar days of making a reservation.

If the study is active, a reservation can be made by following the steps below:

- 1) Log in to https://open.ctsu.org/open/ using your CTEP IAM username and password.
- 2) In order to make a reservation, the patient must have an OPEN patient number. Click on the 'Slot Reservation' tab to create an OPEN patient number, under 'Patients'.
- 3) Using the OPEN patient number 'RESERVE' a slot for that patient.

4) On the 'Create Slot Reservation' page, select the Protocol Number, enter the COG Patient ID, and choose the required stratum (if applicable) in order to obtain a reservation.

Refer to the 'Slot Reservation Site User Guide' posted under the 'Help' tab in OPEN for detailed instructions: https://www.ctsu.org/open/Site\_Resources/Training/Users\_Manual/CTSU-OPEN-SlotReservationSiteUserGuide.pdf

#### 4.4 General Guidelines

Patients may be enrolled on the study once all eligibility requirements for the study have been met. Patients who give informed consent for the protocol in order to undergo screening for eligibility are not considered enrolled and should not be enrolled until the screening is completed and they are determined to meet all eligibility criteria.

Following enrollment, patients should begin protocol treatment within 7 calendar days. Issues that would cause treatment delays should be discussed with the Study Chair. **Patients must not receive any protocol therapy prior to enrollment.** 

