#### 3 PATIENT ELIGIBILITY

## 3.1 Eligibility Inclusion Criteria

Important note: The eligibility criteria listed below are interpreted literally and cannot be waived. All clinical and laboratory data required for determining eligibility of a patient enrolled on this trial must be available in the patient's medical or research record which will serve as the source document for verification at the time of audit.

**3.1.1** Patients must have a history of histologically or cytologically confirmed NBL or osteosarcoma.

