#### 3.1.3 Disease Status

Patients must have measurable or evaluable disease as follows:

- 3.1.3.1 Cohort B1: Confirmed neuroblastoma: measurable NBL/ganglioneuroblastoma (defined as those lesions that can be accurately measured in at least one dimension (longest diameter to be recorded) as ≥ 10 mm with cross sectional imaging (CT scan or MRI), or ≥ 10 mm with calipers by clinical exam). Chest x-ray cannot be used to determine eligibility. Lesions must be MIBG positive, PET avid (if patient has a history MIBG negative disease) or biopsy proven NBL/ganglioneuroblastoma.
- 3.1.3.2 **Cohort B2:** Evaluable NBL (MIBG and/or bone marrow disease only)
- 3.1.3.3 Cohort B3: Measurable osteosarcoma (defined as those lesions that can be accurately measured in at least one dimension (longest diameter to be recorded) as  $\geq 10$  mm ( $\geq 1$  cm) with cross sectional imaging (CT scan, MRI, or calipers by clinical exam). Chest x-ray cannot be used to determine eligibility.
- 3.1.3.4 **Cohort B4:** Patients with relapsed resectable pulmonary osteosarcoma who are scheduled for a surgical resection.

*Note:* Subjects will not have measurable disease due to recently resected pulmonary metastases. Investigational therapy must begin within three weeks of resection. Staged resections are permissible; investigational therapy will be administered in between resections. Patients should receive one cycle of investigational therapy in between resections but can receive additional cycles to accommodate the most appropriate surgical schedule as determined by the treating physicians. Every effort will be made to have at least half of this cohort (five of ten patients) be those requiring a staged resection.

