### 6.2.1.2 Expansion Cohorts (Arm B) Regimen

Once the RP2D is determined from the dose finding cohort, 4 expansion cohorts will be enrolled on Arm B on this study as defined in **Section 6.4**. Expansion cohorts B1-B3 will receive a priming dose of Hu5F9-G4 (magrolimab) (1 mg/kg) on week 1, followed in week 2 with Hu5F9-G4 (magrolimab) administered at RP2D on Day 1 and dinutuximab 17.5 mg/m^2 on Days 2-5. Hu5F9-G4 (magrolimab) will be administered at RP2D on Day 1 of week 3 and 4. A maximum of 12 cycles (see Table 6) can be completed in the absence of DLT or disease progression.

Patients in Arm B Cohort B4 will be enrolled in two subgroups:

- 1. Those who are scheduled for resection of lung lesion(s) (preferred), or those who have recently undergone resection of lung lesion(s) will start the Hu5F9-G4 (magrolimab)/dinutuximab within four weeks of resection as outlined in Section 6.4 and Table 6, and
- 2. Those who are scheduled for resection of lung lesions in a stepwise fashion. Patients in this group will initiate treatment between resections as described in Section 6.4. Prior to resection all patients will receive the Hu5F9-G4 (magrolimab)/dinutuximab as outlined in Table 6. If restart of Hu5F9-G4 (magrolimab)/dinutuximab occurs within four (4) weeks of the last dose of Hu5F9-G4 (magrolimab), the patient will pick up the regimen as per the next scheduled regimen cycle for a maximum of 5 cycles postoperatively.
  - If the restart of the Hu5F9-G4 (magrolimab)/dinutuximab is delayed beyond four weeks of the last dose of Hu5F9-G4 (magrolimab), the post-surgical regimen will be conducted as per Table 7 and will require a re-priming dose of Hu59-G4 (magrolimab).

Every attempt will be made to enroll to the "step-wise resection" subgroup prior to the first resection in order to obtain tissue from the resection for research correlatives. If subjects are enrolled after the initial resection, a request will be made

\*\* Cycles may be repeated as long as the patient does not have unacceptable toxicity (see Section 6.3 or Section Error! Reference source not found.) or disease progression to a maximum of 12 cycles

^ Hydroxyzine (0.5-1 mg/kg, Max dose 50 mg) PO may substitute for diphenhydramine

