#### **6.5.2** Off Study Criteria

- a) Thirty days after the last dose of the investigational agent for patients who develop disease progression during combination therapy.
- b) The fifth anniversary of the date the patient was enrolled on this study, or until disease progression, for patients who complete the maximum number of cycles or who met off protocol therapy criteria in Section 6.5.1 other than disease progression.
- c) Withdrawal of consent for any required observations or data submission.
- d) The patient does not receive protocol treatment after study enrollment.
- e) Patient enrollment onto another COG study with therapeutic (anti-cancer) intent.
- f) Lost to follow-up.
- g) Death

The reason(s) for removal from protocol therapy, the reason(s) for the patient being off study, and the corresponding dates must be documented in the Case Report Form (CRF).

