### 7.2.2 Magrolimab Dosing Guidance for Planned Surgical Procedures

Surgical Procedure	Magrolimab Dose Guidance	
Minimally invasive procedure  (Examples: biopsies (excluding lung/liver), skin/subcutaneous lesion removal, cataract/glaucoma/eye surgery, cystoscopy)	Hold magrolimab dose 3 days prior to procedure and restart 3 days after.	
Moderately invasive procedure  (Examples: lung/liver biopsy, hysterectomy, cholecystectomy, hip/knee replacement, minor laparoscopic procedures, stent/angioplasty)	Hold magrolimab dose 5 days prior to procedure and restart 5 days after.	
Highly invasive procedure  (Examples: CNS/spine surgery, major vascular surgery, cardiothoracic surgery, major laparoscopic surgery)	Hold magrolimab dose 7 days prior to procedure and restart 7 days after.	

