# **9.2.3** Expansion Cohort B4 Primary Endpoint

The primary objective for the expansion cohort B4 is to determine the safety and feasibility of administering Hu5F9-G4 (magrolimab) in combination with dinutuximab to patients that undergo recent resection of metastatic osteosarcoma within three weeks of surgery.

Ten (10) evaluable subjects will be treated with Hu5F9-G4 (magrolimab) and dinutuximab at RP2D. If 3 or more subjects out of the 10 subjects experience complications, the lower bound of the 95% Clopper-Pearson confidence interval on the proportion of complications will be higher than 5%. Thus, if 3 or more subjects out of the 10 subjects experienced complications, the use of Hu5F9-G4 (magrolimab) in combination with dinutuximab after surgery would be considered not feasible.

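### Cohort B4's feasibility question never counts patients who fail to start drug after surgery, and the 7-day start target in Section 4.4 does not fit the cohort's preferred pre-operative enrollment

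*Combined protocol and SAP*

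**What the plan says.** **Start target.** Section 4.4 applies to every cohort: "Following enrollment, patients should begin protocol treatment within 7 calendar days". The next sentence reads: "Issues that would cause treatment delays should be discussed with the Study Chair". No exception is written for B4.

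**Entry to B4.** Criterion 3.1.3.4 describes the cohort as "Patients with relapsed resectable pulmonary osteosarcoma who are scheduled for a surgical resection", and Section 3.1 adds: "The eligibility criteria listed below are interpreted literally and cannot be waived". The note under 3.1.3.4, however, assumes that the metastases have already been removed. Section 6.2.1.2 marks pre-operative entry as preferred and also admits patients whose resection was recent. For the staged subgroup it asks that every attempt be made to enroll to the "subgroup prior to the first resection in order to obtain tissue from the resection for research correlatives", and then provides for those enrolled later. The tissue footnote (19) of the Arm B calendar in Section 11 likewise describes enrollment after a single resection.

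**First drug after surgery.** The limit is three weeks in objective 1.1.3, 3.1.3.4 and 9.2.3. It is four weeks in 6.2.1.2 and, for staged patients, in 6.4. After a unilateral thoracotomy, 6.4 leaves the start to the judgement of the treating physician or surgeon and gives no number of days.

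**Analysis.** Objective 1.1.3 and Section 9.2.3 ask about both safety and feasibility. The only rule in 9.2.3 begins: "Ten (10) evaluable subjects will be treated with Hu5F9-G4 (magrolimab) and dinutuximab at RP2D". Three or more with complications means not feasible. Section 6.5.2(d) lists as a reason for leaving the study: "The patient does not receive protocol treatment after study enrollment".

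**The concern.** Two things fit together badly.

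First, a general enrollment rule written for patients who can be treated at once is applied to a cohort whose preferred path puts an operation between enrollment and first dose. A site following the preferred path will often miss the target. A site that wants to meet it has a reason to enroll late, after the early post-operative course is known.

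Second, whichever way a site enrolls, the analysis has no place for the most direct sign of infeasibility: a patient who had the resection and could not then be given the drugs in time. Such a patient either goes off study untreated or is never enrolled. B4 could be called feasible on ten patients selected because they managed to start, with no record in the result of how many did not.

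**Working it through.** **Inputs.** 7-day target (4.4); start windows of 21 days (1.1.3, 3.1.3.4, 9.2.3) and 28 days (6.2.1.2, 6.4); ten treated evaluable subjects with a cut-off of 3 (9.2.3); removal of untreated enrollees (6.5.2(d)).

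**1. The plan's own figure.** The lower limit of the two-sided 95% Clopper-Pearson interval for x of n is the 0.025 quantile of Beta(x, n - x + 1).
- 3 of 10: Beta(3, 8) gives 6.67%, above 5% as 9.2.3 states.
- 2 of 10: Beta(2, 9) gives 2.52%.

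The cut-off is reproduced. It concerns complications in treated patients and says nothing about failure to start.

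**2. Timeline.** Let surgery be day 0, enrollment day E and first dose day T. The target is T <= E + 7, and a post-operative dose needs T >= 1.
- E = -7 or earlier: T <= 0, so no post-operative first dose meets the target.
- E = -6 to -1: T must fall by post-operative day 1 to 6.
- T = 21 (full three weeks): E >= 21 - 7 = 14.
- T = 28 (full four weeks): E >= 28 - 7 = 21.
- T = 10: E >= 3. T = 14: E >= 7.

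Section 7.2.2 says of highly invasive surgery: "Hold magrolimab dose 7 days prior to procedure and restart 7 days after". If that also governed a first dose, any enrollment at least one day before surgery would take at least 1 + 7 = 8 days and miss the target. But the wording is about interrupting and restarting, so nothing here rests on it.

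**3. Who reaches the ten?**
- Enrolled before the first or only resection, resected, started: eligible to be counted.
- Same, but never started: off study under 6.5.2(d), outside the ten.
- Post-resection entry intended, but failed before enrollment: never seen.
- Started after the window: treated, but 9.2.3 does not say how lateness counts.
- Staged, with trouble at the second resection: already treated between resections (6.4), so 6.5.2(d) does not apply.

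**4. Size, on assumed values.** The documents give no non-start rate. With rate r, ten treated patients come from 10/(1 - r) resected.
- r = 10%: 11.1 resected, 1.1 not counted.
- r = 20%: 12.5 and 2.5.
- r = 30%: 14.3 and 4.3.

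**5. Effect on the complication rule, also assumed.** Suppose a fraction f of patients who would have had a complication never enter. A true rate p then appears as q = p(1 - f) / [p(1 - f) + 1 - p]. For p = 30%, q = 0.225/0.925 = 24.3% at f = 25% and 0.15/0.85 = 17.6% at f = 50%. The chance of 3 or more in 10 is as follows.

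| True rate | f = 0 | f = 25% | f = 50% |
|---|---|---|---|
| 20% | 32.2% | 20.1% | 9.1% |
| 30% | 61.7% | 45.4% | 25.3% |
| 40% | 83.3% | 70.1% | 47.4% |

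**The case against.** The sponsor has good answers to several stronger readings.

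- A reader might infer that B4 patients must be enrolled before surgery. The literal wording of 3.1.3.4 invites this, but its own note, 6.2.1.2 and the calendar footnote all allow entry after resection.
- A reader might infer that the rules cannot all be met. Section 4.4 says should, not must, and sends delays to the Study Chair. Post-operative entry can meet every window.
- A reader might infer that keeping to the target admits only recovered patients. Enrollment on day 3 for a day-10 start complies, and no eligibility criterion requires recovery from surgery.
- A reader might infer that surgical failures drop out on every route. That is not so for the second staged resection, and 3.1.3.4 aims for five of the ten to be staged.
- A reader might infer that late entry loses the tissue. Section 6.2.1.2 requests archived tissue instead. Only prospective collection at the first resection is weakened.

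It can also be said that a treated denominator is the right one for complications of treatment, and that 6.5.2 already requires off-study reasons on the case report form. Both are true. Neither supplies a feasibility result: the reasons are recorded, but no analysis uses them. The Study Chair route suits individual delays; here the preferred path of a whole cohort would need it routinely. Finally, the missing count comes from 9.2.3 and 6.5.2(d) and would remain without the 7-day target, so it is argued here as a separate point.

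**Conclusion.** Two limited conclusions hold. The 7-day target in 4.4 does not fit B4's preferred route: enrollment a week or more before surgery cannot meet it, and using the full three-week window on target means enrolling on post-operative day 14 or later (day 21 for four weeks). That tilts entry towards patients without early post-operative problems; it does not restrict entry to them. More important, feasibility is part of B4's primary question, yet failure to start after the first or only resection never counts against it.

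The timeline follows from the documents alone. The size of the effect does not. The 1.1 to 4.3 uncounted failures rest on an assumed 10% to 30% non-start rate, and the loss of sensitivity in the table rests on an assumed 25% or 50% selection. Neither is evidence that this has happened. The change should be made because it is cheap and removes a selection bias from the feasibility conclusion. The stronger readings listed above are not supported.

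**What to change.** 1. **Section 9.2.3.** Keep the ten treated patients and the 3-of-10 rule for complications. Add a feasibility proportion. Its denominator is all B4 patients enrolled before their first or only resection who undergo it; its numerator is those who start within the protocol window. Keep non-starters, with their reasons, in that denominator despite 6.5.2(d). Report it with an exact interval, which will be wide at this size.
2. **Entry timing.** Record whether each B4 patient was enrolled before or after the first or only resection, and report post-resection entries separately. They cannot inform the proportion, because patients who failed before entry were never seen.
3. **Wording.** Reconcile 4.4 with the B4 passages. Reconcile the three-week statements (1.1.3, 3.1.3.4, 9.2.3) with the four-week statements (6.2.1.2, 6.4), so that one window defines the endpoint; 4.4 cannot refer to a B4 window until this is done. Which window applies is for the sponsor to settle.

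The cost is an amendment to these sections, one entry-timing item in the data and a short added analysis; off-study reasons are already collected. A few enrolled patients who never receive drug will be reported, and the feasibility figure may look less favourable.
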